The goal of the VTBs to design a set of best options for each specific patient, considering not just tumor location, histopathology, or a molecular marker, but rather take a holistic approach that integrates all available information with a large database of patients with treatments and clinical outcomes. In that sense, each patient is an n-of-1 and forms their own arm within a large registry. The VTB receives case information and options prepared by a cancer biologist with support from the xCures AI system which is informed by the XCELSIOR dataset and employs state-of-the-art analytic techniques to identify similar patients and use information about their treatments, treatment-decision process, and safety or effectiveness outcomes to inform treatment recommendation. After that, the assigned VTB members review the case and available information, apply their own expert knowledge about pathways or mechanisms, and then prepare a limited set of options for treatments, or recommend additional testing. This information is provided to patients and their oncologists as a set of options for consideration with supporting evidence only. The patient and their doctor ultimately make a treatment decision, as they do already in normal clinical care. The VTB will gather information about what treatment they choose and why, and then incorporate that information into the analytic model and utilize it to inform treatment options for future patients. This iterative process is important to develop personalized medicine information in a systematic way that puts the individual patient outcome at the fore.

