2.4.1 PATIENT OPTIONS CORE

Experts on the VTB review the case and develop an equipoise set of options that have the strongest rationale for success. The VTB platform created by Cancer Commons will use analytic techniques to provide additional information to the patient and their physician about the known risks and effectiveness of each treatment in the equipoise set. Specifically, the patient's physicians will be provided information about (a) when particular treatments were previously used or rejected by other clinicians, including cohort level and non-PHI individual case-level details, and the rationale(s) for using or rejecting treatments in these patients, and (b) an explanation of the information that could be gained through the use of each treatment expressed as an information to information-gain ratio, which augments the description of the global benefits by quantifying how much can be learned from different treatment options within the equipoise set.

The system uses machine learning to facilitate the recollection of recommendations made for similar patients in the past, but human expertise oversees this at multiple stages. The patient and their doctor can then review the suggestions and supporting evidence and decide without concern about access, knowing that xCures' Patient Access Core team is available to help facilitate access to the selected options. That data will be collected and if a similar patient is identified in the future, it becomes available for reference. Using a Bayesian non-parametric clustering model for example to conduct patient grouping, the system and the VTB experts can learn as new data is generated. The approach includes a prospective element, since the clustering model can create explicit forecasts for patient trajectory with and without various treatment options, for example using Bayesian Additive Regression Trees. This allows for statistically valid inferences to be developed about optimal treatments for specific patient subgroups, and this can be used for supportive evidence both for Patient Access Core operations and in published literature.

This group of patient-centric registries will advance the knowledge base necessary to implement what the FDA describes as patient-focused drug development in oncology. Specifically, they describe this as doing a better job incorporating the patient's voice in drug development, including but not limited to:

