In clinical practice, and for patients enrolled in the XCELSIOR protocol, if a patient has multiple mutations or molecular markers that are logical therapeutic targets, the VTB may propose targeting any or all in combination. Treatments with the strongest rationale including molecular, genomic, clinical, and other supporting evidence may all be considered to create a patient-specific specific plan. These patient-specific plans are a hypothesis and through the analytics within XCELSIOR have both supporting evidence and a prospective forecast for disease trajectory. The plan is not limited to single agents, or even to approved treatments. Patients' best option may be a clinical trial or compassionate use. XCELSIOR supports both. Patients best option may be additional diagnostic testing before a treatment plan is defined. In such cases, XCELSIOR will support additional testing. This is a fundamentally patient-centric approach in which the treatments are matched to the patient rather than matching a patient to clinical trial. Within the XCELSIOR registry model, the patient isn't allocated to specific trial arm that is limited by pre-specification at all; their arm is treatment that their clinician decides will give them the best chance of response. The purpose of the registry is to create a systemic framework so that these experiences, which occur in clinical practice every day, can be mined for data that can improve patient care, by identifying which treatments work or do not work for patients based on identifiable factors.

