5.2.2 VIRTUAL TUMOR BOARD PROCESS

Following registration and consent, XCures acting alone or on behalf of a partner or collaborator will contact the patient to begin collection and abstraction of their medical information into a patient summary to be provided to the VTB. This process includes identification of similar patients medically-logical treatment options, including clinical trials, that have been suggested by the VTB for similar patients or have otherwise been identified as medically logical for similar patients, with relevant information from the study Leaderboard, if available. The

completed summary is then submitted to at least three VTB members selected based on their availability and expertise for review. The VTB using will review the case, options, and discuss using on- or off-line technology support, to reduce the options into a list of best options at clinical equipoise. Rationale capture for addition, inclusion, or removal is collected for global learning analysis. Additional rounds of review and discussion may be undertaken to further refine the option list and VTB members may request additional information, including review of source records, to support their review. Once the option set is reduced the patient utility is applied and simulation analysis is run to assess the global information gain value of the options in the equipoise set. Together these are provided to the VTB to determine whether they then wish to update their selection of options. Finally, the refined option list, with supporting information and rationales, plus information gain value and alignment with patient preference are provided to the patient and their doctor for consideration.

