8.1.2 EQUIPOISE OPTIONS SET AND RESPONSE MEASUREMENT

XCures acting alone, on behalf of, or with partner or collaborator currently maintains a curated list of treatment options for various advanced and recalcitrant cancers. This includes both regimens and clinical trials. In addition, treatment options suggested during consultation from VTB experts is incorporated with rationale. For example, if a patient with a tumor that is highly expressing a particular protein or gene for which there is a targeted therapy receives a suggested option from the VTB that includes off-label use for the targeted therapy due to the presence of amplification of the drug target, that becomes part of the global option set and can be matched to future patients with similar characteristics.

Matching of potential treatments to patients within clusters is accomplished through the VTB process, in which a cancer biologist at XCures acting alone, on behalf of, or with partner or collaborator curates the patient's case

information and assembles a list of possible treatment options based on rationales for review by the VTB. The VTB can refine this list or add other options. Once implemented, the patient cluster model will facilitate this process by quickly identifying options and outcomes for similar patients.

The VTB curates individual treatment option sets with analytic support to evaluate equipoise. Equipoise is defined as an overlap in the calculated treatment outcome variance among options considered in relation to similar patients defined via clustering.

Reporting of treatments will involve a filtered "Leaderboard" based on how various options have performed for different clusters of patients. The following characteristics may be calculated as the leaderboard parameters of treatment options both overall and in relation to specific patient clusters, including:

- Number of times treatment was recommended by the VTB
- Number of times a VTB-recommended treatment was chosen by a patient's doctor
- Number of patients actively on the treatment
- Efficacy signal to date using Bayesian model that can incorporate external information
- Safety/Tolerability signal to date
- Information Score

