8.1.5 SAMPLE SIZE CONSIDERATIONS

Because this registry is not hypothesis-driven, formal prospective sample-size calculations are not required.

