8.1.6 POPULATIONS FOR ANALYSES

The entire research database will be subject to classification analysis using various machine learning models to build an evolving and logical framework for patient similarity using all available baseline co-variate information. Cluster models may include Bayesian hierarchical models, K Nearest Neighbor, Random Forest models, and Deep Neural Networks. The purpose of population analysis is to determine the relative importance of baseline co-variates in support of individual treatment matching. Each patient will be algorithmically matched to their nearest similar patients for the purposes of identifying treatment and response in similar patients. As new information develops continuously, the cluster algorithm will be recalculated to incorporate new information gain.

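### The leaderboard in 8.1.2 provides for an overall efficacy and safety ranking of clinician-chosen options, so case-mix can be read as treatment effect; selection can also remain within clusters

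*Protocol*

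**What the plan says.** - **Allocation.** Under Protocol 2.4.1 there are no assigned arms; for each patient, "their arm is treatment that their clinician decides will give them the best chance of response".
- **Level of comparison.** Protocol 8.1.2 describes a leaderboard filtered by patient cluster, but its parameters, including the efficacy and safety/tolerability signals to date, may be computed at both levels: "The following characteristics may be calculated as the leaderboard parameters of treatment options both overall and in relation to specific patient clusters". The efficacy entry comes from a Bayesian model. The same section then says, without a conditional, that each leaderboard item will be scored by a pairwise ranking algorithm.
- **Patient similarity.** Protocol 8.1.6 uses machine learning to "build an evolving and logical framework for patient similarity using all available baseline co-variate information".
- **Determinants of treatment.** Protocol 5.2.2 has a final option list go to patient and doctor, and on the board's reasons it says: "Rationale capture for addition, inclusion, or removal is collected for global learning analysis". Protocol 2.2.2 adds: "The VTB will gather information about what treatment they choose and why". That sentence continues by feeding the information into the analytic model.
- **Use of the results.** Under 5.2.2, leaderboard information goes into the case summary for the next VTB review where available. Under 7.4, the virtual data monitoring committee may act on safety and effectiveness signals within and among subgroups.

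**The concern.** When clinicians choose the treatment, a difference in outcome between two options mixes what the options do with who received them. At the overall level nothing in 8.1.2 conditions on tumour type or prognosis, so an option used mainly in a better-prognosis tumour rises for that reason alone. Within a cluster the same mechanism can act on any feature that differs between members and drives both choice and outcome.

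More patients do not help. Section 8.1.2 expects the variance of signals to fall as data accrue, but this bias does not fall with it, so a misplaced ranking would simply look firmer. Because leaderboard information can reach later VTB reviews, a biased rank could also influence which options later patients are offered.

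**Working it through.** The protocol gives no effect size, error rate or number per option ("Because this registry is not hypothesis-driven, formal prospective sample-size calculations are not required", 8.1.5), so there is no figure to reproduce. Every input below is an assumption for illustration, and the true difference between options is zero throughout.

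**1. Overall level.** Two tumour types have response *r_lo* = 5% and *r_hi* = 25%, the same under either drug. Drug B is used 80:20 across them (mostly low-response), drug A 20:80.
- B: 0.8 × 5% + 0.2 × 25% = 9%.
- A: 0.2 × 5% + 0.8 × 25% = 21%.
- With mirror-image use and larger share *w*, the spurious difference is (2*w* − 1) × (*r_hi* − *r_lo*) = 0.6 × 20 = 12 points. At 60:40 it is 0.2 × 20 = 4 points; at 90:10 it is 0.8 × 20 = 16 points.
- Standardised to a common 50:50 mix, both drugs give 0.5 × 5% + 0.5 × 25% = 15%.

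This uses pooled proportions. A Bayesian model with no case-mix term would carry the same bias; one with such a term need not.

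**2. Within a cluster.** A feature not captured by the cluster holds in half the members. Response is 30% with it and 10% without. Option A is chosen by 70% of those with it and 30% of those without.
- A: 0.7 × 30% + 0.3 × 10% = 24%.
- B: 0.3 × 30% + 0.7 × 10% = 16%.
- Spurious difference: 8 points.

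The chance of a two-sided 5% test favouring A is Φ[(0.08 − 1.96 × SE₀)/SE₁], with SE₀ = √(2 × 0.20 × 0.80/n) and SE₁ = √[(0.24 × 0.76 + 0.16 × 0.84)/n]:

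| n per option | Chance |
|---|---|
| 50 | 17% |
| 100 | 29% |
| 200 | 52% |
| 400 | 81% |

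Choice splits of 60:40 to 80:20, with response of 20% versus 10% up to 40% versus 10%, give spurious differences of 0.2 × 10 = 2 to 0.6 × 30 = 18 points. With no selection (50:50) the difference is zero.

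**3. Restricting to patients offered both options.**
- *Selection at the offer only.* Suppose 40% are offered only B and respond at 10%; the other 60% are offered both, split evenly and respond at 30%. Crude rates are A 30% and B (0.3 × 30% + 0.4 × 10%)/0.7 = 18.6%. Among those offered both, the rates are 30% and 30%.
- *Selection at the choice.* If the pattern of step 2 holds among patients offered both, they again show 24% versus 16%.

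The restriction therefore removes selection at the offer and leaves selection at the choice untouched.

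**The case against.** The strongest reply is that the protocol has more than a crude table. Clusters draw on all baseline covariates (8.1.6). Signals are also scored by paired time to progression or to treatment switching and against forecasts (8.1.4). Individual response may be modelled with Bayesian Additive Regression Trees (8.1.7). Leaderboard parameters are optional, and signals go to human review (8.1.4). Adjustment sets usually belong in a statistical analysis plan, which is not at hand.

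Much of this stands, and it rules out several stronger readings that a reader might infer:

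- *That options are compared only overall or by cluster, and that recorded reasons enter no outcome comparison.* Section 2.2.2 sends choice and reason into the analytic model, 5.2.1 and 8.1 plan research linking rationale to outcomes, and 8.1.4 scores signals partly on agreement with the VTB rationale. No adjustment method is given, but that is not exclusion.
- *That an option set exists for every patient.* VTB use is optional (synopsis), and patients may choose an option that the VTB did not present (2.2.4).
- *That the protocol calls leaderboard comparisons valid inference.* The claim in 2.4.1, "This allows for statistically valid inferences to be developed about optimal treatments for specific patient subgroups", follows a sentence on regression-tree forecasts, not the leaderboard.
- *That ranking only among patients offered both options would cure the problem.* Step 3 shows otherwise. Clusters that 2.2.9 itself expects to be very small may also leave many such contrasts empty.

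The safeguards do not answer the narrower point. The forecast is the trajectory of the patient's own cluster (5.1.1.1), so it cannot correct for selection on features that vary inside it. The regression-tree model is optional. The protocol ties none of these tools to the ranking as control for indication, and clustering cannot protect a score computed across clusters.

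**Conclusion.** The point holds for the overall efficacy and safety ranking: followed as written, 8.1.2 permits a ranking that mixes case-mix with treatment effect. It holds as a risk, not a certainty, within clusters, where residual selection is reduced in part by the tools above. The size is illustrative: 12 points overall (4 to 16 over the usage splits shown) and 8 points within a cluster (2 to 18), all with no true difference. These rest on assumed response rates and choice patterns and on unadjusted proportions. An analysis model that conditioned on tumour type, prognosis and choice of option would shrink them. The missing adjustment set is not itself a fault of the protocol; the stated overall level of comparison, combined with pairwise ranking, is. The change should be made, but it does not call the registry's data collection into question.

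**What to change.** 1. In 8.1.2, give no overall efficacy or safety ranking, or standardise it to one common, stated mix of clusters. Overall counts of recommendations and use can stay as description.
2. Base within-cluster rankings on the covariate-adjusted individual-level model of 8.1.7, including baseline prognosis and the estimated propensity for the option.
3. For patients who used the VTB, add a sensitivity comparison of two options among those whose recorded final option set held both. State beside it that selection at the choice stage and unrecorded reasons remain.

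Items 1 and 2 need mainly changes to the analysis wording. Item 3 needs the option set in analysable form; the data elements in 7.1.4 do not name it, so some coding work should be expected. The statistical price is fewer patients per contrast, wider intervals and some contrasts that cannot be estimated, which should be reported as such.

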8.1.3 PATIENT UTILITY ANALYSIS

One of the goals of XCELSIOR is to use quantitative methods to incorporate patient preference, including goals and risk-tolerance into the analysis of treatment options. This approach complements the goal of assessing and monitoring global information gain. Information and uncertainty in treatment is typically expressed as variance. Similarly, in economics, including behavioral economics variance equates to risk. This suggests that by incorporating a patient goals and preferences survey using conjoint regression, a utility function expressed mathematically can be incorporated into the scoring of possible treatments and that this scoring method will closely align with information gain within the overall system. The benefit of this approach is that it can be used to help reduce the number of equipoise treatment options by adding alignment (a distance measurement between two functions—the treatment information gain function calculated for a specific patient with the patient's utility function derived from a conjoint analysis survey at registration). This information may be provided to the patient's physician and/or VTB to help them refine their considerations and incorporate patient-specific goals and values. This approach relies on a series of simple paired choice questions to derive a complex function and unlike some quantitative methods reduces the need to either patients or doctors to have high-level numeracy (Politi et al., 2012).

The goal is to help ensure that patients receive treatments that align with their goals. It is hypothesized that risk tolerance is correlated with overall information gain, and this will be an area of analysis within XCELSIOR. A similar approach was implemented by Mohamed et al (ISPOR conference poster) for renal cell carcinoma patients. In that study, the most important goal resulting from conjoint regression of the paired choice options was the prospect of a month extension of PFS was worth a 1% increase in risk of death from a fatal adverse drug effect.

8.1.4 ANALYTIC SIGNAL DETECTION

General and disease-specific response signals will be detected using traditional query detection methods augmented with both human expertise and machine learning techniques. Signals will be detected by monitoring routine and spontaneous assessments collected from the medical record and augmented with surveys, which may include labs, imaging, patient- and physician-reported questionnaires, and other information such as treatment switching or progression declarations. Signals may be detected from changes in magnitude or rate of change and scored based on direction of the change and correlation with the VTB treatment rationale. Once detected, potential signals will be escalated for human review by a scientist, medical director, or the VTB/vDMC. Signals may be mapped to response criteria, for example RANO. Spontaneous response measures, such as time-to-progression, time-to-treatment switching, and/or changes to anti-cancer therapy regimen will be detected and scored using paired TTP or TTTS and in relation to baseline forecasts.

It should be noted that signal detection in non-linear networked systems, such as the composite responder analysis integrating numerous non-linear assessments into a network of aggregated n-of-1 experiments, benefits from a certain level of "noise" within the network. This phenomenon is called stochastic resonance and is widely used in telecommunications and other networked systems to amplify weak signals in a noisy environment. Such approaches may be considered for enhancing signal detection in XCELSIOR.

8.1.5 SAMPLE SIZE CONSIDERATIONS

Because this registry is not hypothesis-driven, formal prospective sample-size calculations are not required.

8.1.6 POPULATIONS FOR ANALYSES

The entire research database will be subject to classification analysis using various machine learning models to build an evolving and logical framework for patient similarity using all available baseline co-variate information. Cluster models may include Bayesian hierarchical models, K Nearest Neighbor, Random Forest models, and Deep Neural Networks. The purpose of population analysis is to determine the relative importance of baseline co-variates in support of individual treatment matching. Each patient will be algorithmically matched to their nearest similar patients for the purposes of identifying treatment and response in similar patients. As new information develops continuously, the cluster algorithm will be recalculated to incorporate new information gain.

8.1.7 STATISTICAL ANALYSES

Because the symptoms of recalcitrant cancers can be diverse, an integrated responder analysis approach will be used for signal detection. This approach will integrate symptomatic, clinical, laboratory, imaging, or other measures of response into a responder analysis framework. This approach has been used successfully in rare disease studies that are characterized by few patients and diverse symptoms.

Because individuals in XCLESIOR are likely to have few treatment opportunities due to a short expected lifespan, the goal of responder analysis is to identify response early, or in the absence of response work with the patient, their physician and the VTB to try the next equipoise option or re-run the VTB process quickly to start an alternative therapy. This approach should enable XCELSIOR to observe a series of n-of-1 treatments within patients. These changes occur naturalistically during the treatment of cancer patients and will be evaluated individually and in an aggregated n-of-1 analysis for safety and effectiveness signal detection. Effectiveness signal detection may be based on Bayesian models that incorporate hierarchical clustering with additive regression trees to both group patients in a continuously learning model, while also implementing a flexible and efficient model layer for estimating individual treatment response prospectively using Bayesian Additive Regression Trees (Logan et al., 2018).

Analyses may be conducted to assess hypotheses for both the safety and/or effectiveness of various treatments along or in combination for different patient subgroups, based on the emergence of data suggesting new hypotheses. VTB members and interested researchers may propose research plans and analyses to XCures acting alone, on behalf of, or with partner or collaborator. Such analyses will be reviewed by XCures acting alone, on behalf of, or with partner or collaborator and may be undertaken in accordance with the publication policy in Section 5.1.7.

